5.4.3.2 Pregnancies in Female Partners of Male Patients

Male patients will be instructed through the Informed Consent Form to immediately inform the investigator if their partner becomes pregnant during the study or within 30 days after the final dose of venetoclax. 5 months after the final dose of atezolizumab. or 6 months after the final dose of carboplatin or etoposide, whichever occurs last. A paper Clinical Trial Pregnancy Reporting Form should be completed and submitted to the Sponsor or its designee immediately (i.e., no more than 24 hours after learning of the pregnancy), either by faxing or by scanning and emailing the form using the fax number or email address provided to investigators. Attempts should be made to collect and report details of the course and outcome of any pregnancy in the partner of a male patient exposed to study treatment. When permitted by the site, the pregnant partner would need to sign an Authorization for Use and Disclosure of Pregnancy Health Information to allow for follow-up on her pregnancy. If the authorization has been signed, the investigator should submit a Clinical Trial Pregnancy Reporting Form when updated information on the course and outcome of the pregnancy becomes available. An investigator who is contacted by the male patient or his pregnant partner may provide information on the risks of the pregnancy and the possible effects on the fetus, to support an informed decision in cooperation with the treating physician and/or obstetrician.

Venetoclax—F. Hoffmann-La Roche Ltd Page 132 of 214 Protocol GO41864, Version 2

5.4.3.3 Abortions

A spontaneous abortion should be classified as a serious adverse event (as the Sponsor considers abortions to be medically significant), recorded on the Adverse Event eCRF, and reported to the Sponsor immediately (i.e., no more than 24 hours after learning of the event; see Section 5.4.2).

If a therapeutic or elective abortion was performed because of an underlying maternal or embryofetal toxicity, the toxicity should be classified as a serious adverse event, recorded on the Adverse Event eCRF, and reported to the Sponsor immediately (i.e., no more than 24 hours after learning of the event; see Section 5.4.2). A therapeutic or elective abortion performed for reasons other than an underlying maternal or embryofetal toxicity is not considered an adverse event.

All abortions should be reported as pregnancy outcomes on the paper Clinical Trial Pregnancy Reporting Form.

5.4.3.4 Congenital Anomalies/Birth Defects

Any congenital anomaly/birth defect in a child born to a female patient exposed to study treatment or the female partner of a male patient exposed to study treatment should be classified as a serious adverse event, recorded on the Adverse Event eCRF, and reported to the Sponsor immediately (i.e., no more than 24 hours after learning of the event; see Section 5.4.2).

5.5 FOLLOW-UP OF PATIENTS AFTER ADVERSE EVENTS

5.5.1 Investigator Follow-Up

The investigator should follow each adverse event until the event has resolved to baseline grade or better, the event is assessed as stable by the investigator, the patient is lost to follow-up, or the patient withdraws consent. Every effort should be made to follow all serious adverse events considered to be related to study treatment or trial-related procedures until a final outcome can be reported.

During the study period, resolution of adverse events (with dates) should be documented on the Adverse Event eCRF and in the patient's medical record to facilitate source data verification.

All pregnancies reported during the study should be followed until pregnancy outcome.

5.5.2 Sponsor Follow-Up

For serious adverse events, adverse events of special interest, and pregnancies, the Sponsor or a designee may follow up by telephone, fax, email, and/or a monitoring visit to obtain additional case details and outcome information (e.g., from hospital discharge summaries, consultant reports, autopsy reports) in order to perform an independent medical assessment of the reported case.

5.6 ADVERSE EVENTS THAT OCCUR AFTER THE ADVERSE EVENT REPORTING PERIOD

After the end of the reporting period for serious adverse events and adverse events of special interest (defined as 90 days after the final dose of study treatment or until initiation of new systemic anti-cancer therapy, whichever occurs first), all deaths, regardless of cause, should be reported through use of the Long-Term Survival Follow-Up eCRF.

In addition, if the investigator becomes aware of a serious adverse event that is believed to be related to prior exposure to study treatment, the event should be reported through use of the Adverse Event eCRF. However, if the EDC system is not available, the investigator should report these events directly to the Sponsor or its designee, either by faxing or by scanning and emailing the paper Clinical Trial Serious Adverse Event of Special Interest Reporting Form using the fax number or email address provided to investigators.

5.7 EXPEDITED REPORTING TO HEALTH AUTHORITIES, INVESTIGATORS, INSTITUTIONAL REVIEW BOARDS, AND ETHICS COMMITTEES

The Sponsor will promptly evaluate all serious adverse events and adverse events of special interest against cumulative product experience to identify and expeditiously communicate possible new safety findings to investigators, IRBs, ECs, and applicable health authorities based on applicable legislation.

To determine reporting requirements for single adverse event cases, the Sponsor will assess the expectedness of these events through use of the reference safety information in the documents listed below:

Drug	Document
Atezolizumab	Atezolizumab Investigator's Brochure
Venetoclax	Venetoclax Investigator's Brochure

The Sponsor will compare the severity of each event and the cumulative event frequency reported for the study with the severity and frequency reported in the applicable reference document.

Reporting requirements will also be based on the investigator's assessment of causality and seriousness, with allowance for upgrading by the Sponsor as needed.

The Sponsor will monitor safety data during the study. An aggregate report of any clinically relevant imbalances that do not favor the test product will be submitted to health authorities

6. STATISTICAL CONSIDERATIONS AND ANALYSIS PLAN

6.1 DETERMINATION OF SAMPLE SIZE

The estimated sample size of the dose-escalation phase follows from the doseescalation rules of a standard 3+3 algorithm. It is anticipated that enrollment of two cohorts of 3–6 patients each in the maintenance phase, as well as up to five cohorts of 3–6 patients each in the induction phase, for a total of 18–42 patients, will be required to establish the RP2D for maintenance (RP2D-M) and the RP2D for the induction setting (RP2D-I) during the dose-escalation phase.

A sample of 20 patients will be sufficient to provide adequate precision for the point estimates. Assuming an observed ORR of 80% for the induction plus maintenance setting (Arm B), with 20 patients, the lower bound of the two-sided 80% CI will rule out a probability of response of 63%. Assuming an observed ORR of 5% for the maintenance-only setting (Arm A), with 20 patients, the lower bound of the two-sided 80% CI will rule out a probability of response of 0%.

An 80% CI for true underlying ORR values of 0.05, 0.1, 0.7, 0.75, and 0.8 are provided in Table 13.

Table 13Operating Characteristics for Proposed Study Design for Several
Possible True Underlying Overall Response Rate

		Tru	e Underlying	ORR	
	5%	10%	70%	75%	80%
80% confidence interval for true ORR	(1%, 18%)	(3%, 24%)	(53%, 83%)	(59%, 87%)	(64%, 91%)

^a Confidence intervals are based on the assumption that the point estimate is equal to the true underlying value of the objective response rate (ORR) in each column.

For a given adverse event with a true rate of 10%, 5%, or 1%, the probability of observing at least one such event in a cohort of 20 patients is 87.8%, 64.2%, and 18.2%, respectively. Table 14 describes exact 90% CIs for a range of observed proportions of adverse events based on a sample size of 20 patients.

Exact 90% Confidence Interval for the Potential Adverse Event Rates
(0%, 16%)
(0%, 22%)
(2%, 28%)
(7%, 40%)
(14%, 51%)
-

Table 14 90% Confidence Interval Estimates for Potential Adverse Event Rates

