Primary Analysis

The analysis population for the efficacy analyses will consist of all enrolled patients in the doseexpansion cohort, with patients grouped according to their assigned dose levels and treatment schedules.

The primary efficacy objective for the Phase Ib dose-expansion cohort is to evaluate the preliminary efficacy of venetoclax in combination with atezolizumab as maintenance therapy or venetoclax in combination with atezolizumab, carboplatin, and etoposide as induction therapy followed by venetoclax plus atezolizumab as maintenance therapy on the basis of the following endpoint:

 ORR, defined as the proportion of patients with a CR or PR on two consecutive occasions ≥ 4 weeks apart, as determined by the investigator according to RECIST v1.1 criteria.

Patients with no disease assessments for any reason will be classified as non-responders. An estimate of ORR with 90% exact confidence interval (CI) will be presented using the method of Pearson Clopper.

Interim Analyses Planned Interim Analyses None planned.

Abbreviation	Definition
ADA	anti-drug antibody, also called anti-therapeutic antibody
AML	acute myeloid leukemia
Bcl-2	B-cell lymphoma 2
CBR	clinical benefit rate
CE	carboplatin and etoposide
CI	confidence interval
CLL	chronic lymphocytic leukemia
CR	complete response
CRCL	creatinine clearance
СТ	computed tomography
CTCAE	Common Terminology Criteria for Adverse Events
ctDNA	circulating tumor DNA
DDI	drug-drug interaction
DLTs	dose-limiting toxicities
DOR	duration of response
EBV	Epstein-Barr virus
EC	Ethics Committee
ECOG	Eastern Cooperative Oncology Group
eCRF	electronic Case Report Form
EDC	electronic data capture
EORTC	European Organisation for Research and Treatment of Cancer
ER	estrogen receptor
ES-SCLC	extended stage small cell lung cancer
FDA	Food and Drug Administration
FFPE	formalin-fixed paraffin-embedded
G-CSF	growth-colony stimulating factor
GFR	glomerular filtration rate
HBcAb	hepatitis B core antibody
HBsAg	hepatitis B surface antigen
HBV	hepatitis B virus
HCV	hepatitis C virus
HIPAA	Health Insurance Portability and Accountability Act
HR	hazard ratio
IBM	ideal body mass
ICH	International Council for Harmonisation

LIST OF ABBREVIATIONS AND DEFINITIONS OF TERMS

Abbreviation	Definition
IHC	immunohistochemistry
IMP	investigational medicinal product
IND	Investigational New Drug (Application)
IRB	Institutional Review Board
IRR	infusion-related reactions
IV	intravenous
IxRS	interactive voice or web-based response system

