6.5.1 Primary Efficacy Endpoint

The primary efficacy objective for the Phase Ib dose-expansion cohort is to evaluate the preliminary efficacy of venetoclax in combination with atezolizumab as maintenance therapy or venetoclax in combination with atezolizumab, carboplatin, and etoposide as induction therapy followed by venetoclax plus atezolizumab as maintenance therapy on the basis of the following endpoint:

 ORR, defined as the proportion of patients with a CR or PR on two consecutive occasions ≥4 weeks apart, as determined by the investigator according to RECIST v1.1 criteria.

Patients with no disease assessments for any reason will be classified as nonresponders. An estimate of ORR with 90% exact CI will be presented using the method of Pearson Clopper.

6.5.2 Secondary Efficacy Endpoints

The secondary efficacy objective for the Phase Ib dose-expansion cohort is to evaluate the preliminary efficacy of venetoclax in combination with atezolizumab as maintenance therapy or venetoclax in combination with atezolizumab, carboplatin, and etoposide as induction therapy or venetoclax and atezolizumab as maintenance therapy on the basis of the following endpoints:

- DOR
- PFS
- OS
- PFS rate at 6 months
- OS rate at 1 year

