6.5.2.4 Progression-Free Survival Rate at 6 Months

PFS rate at 6 months, defined as the proportion of patients who have not experienced disease progression, relapse, or death from any cause at 6 months, as determined by the investigator according to RECIST 1.1 criteria.

The PFS rate at 6 months will be estimated using the Kaplan-Meier methodology. A two-sided 90% CI of the PFS rate at 6 months will be presented based on Greenwood's method of estimating the variance of the KM estimate.

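### Section 6.1 and Table 13 justify n = 20 with 80% intervals, but the primary ORR will be reported with a 90% exact interval, under which 16/20 does not rule out 63%

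*Combined protocol and SAP*

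**What the plan says.** Section 6.1 opens its case for the expansion cohort with "A sample of 20 patients will be sufficient to provide adequate precision for the point estimates". It then takes an observed ORR of 80% in the induction-plus-maintenance setting and states that "with 20 patients, the lower bound of the two-sided 80% CI will rule out a probability of response of 63" per cent. For the maintenance-only setting it takes an observed ORR of 5% and says that 0% is ruled out, again with an 80% interval. Table 13 gives 80% intervals for five rates: (1%, 18%) at 5%, (3%, 24%) at 10%, (53%, 83%) at 70%, (59%, 87%) at 75% and (64%, 91%) at 80%.

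Section 6.5.1 fixes the primary analysis at a different level: "An estimate of ORR with 90% exact CI will be presented using the method of Pearson Clopper". The Primary Analysis paragraph of the synopsis says the same.

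Other parts of the plan also use 90%. Section 6.1 itself says "Table 14 describes exact 90% CIs for a range of observed proportions of adverse events based on a sample size of 20 patients". Section 6.5.2.4 says a "two-sided 90% CI of the PFS rate at 6 months will be presented", and Section 6.5.2.5 applies the same method to the 1-year survival rate.

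**The concern.** The sample size is justified by precision alone, so the interval used for planning should be the interval that will be reported. Here the planning interval is narrower. The level of 80% appears only in the ORR justification, and no section says why it was chosen.

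What is at stake is the claim about the result that the plan itself assumes. If the trial observes 16 responders in 20, Section 6.1 leads the reader to expect that 63% is excluded, but the interval in the report will contain 63%. Section 6.1 is the only quantitative support in the plan for calling the precision of the primary endpoint adequate.

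**Working it through.** **Inputs.** n = 20 and an assumed ORR of 80%, that is 16/20 (Section 6.1); planning level 80% (Section 6.1, Table 13); reporting level 90%, Clopper-Pearson (Section 6.5.1, synopsis).

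**Formula.** For x responders out of n and two-sided level 1 − α:
- lower limit = α/2 quantile of Beta(x, n − x + 1)
- upper limit = 1 − α/2 quantile of Beta(x + 1, n − x)

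Equivalently, a rate p is excluded from below when P(X ≥ x | n, p) < α/2.

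**Step 1: reproduce the plan, then change only the level.** Widths are in percentage points and were taken before rounding.

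| Responders | Table 13 | 80% exact | 90% exact | Width at 80% | Width at 90% |
|---|---|---|---|---|---|
| 1/20 | (1%, 18%) | 0.5% to 18.1% | 0.3% to 21.6% | 17.6 | 21.4 |
| 2/20 | (3%, 24%) | 2.7% to 24.5% | 1.8% to 28.3% | 21.8 | 26.5 |
| 14/20 | (53%, 83%) | 53.3% to 83.4% | 49.2% to 86.0% | 30.1 | 36.8 |
| 15/20 | (59%, 87%) | 58.5% to 87.3% | 54.4% to 89.6% | 28.8 | 35.2 |
| 16/20 | (64%, 91%) | 63.9% to 91.0% | 59.9% to 92.9% | 27.0 | 33.0 |

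The 80% column matches all five Table 13 entries to the nearest whole per cent. The method behind the table is therefore Clopper-Pearson, and its arithmetic is right. The lower bound of 63.9% supports the statement about 63% at that level.

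**Step 2: test 63% directly.** P(X ≥ 16 | 20, 0.63) = 0.086. This is below 0.10, the tail of an 80% interval, so 63% is excluded there. It is above 0.05, the tail of a 90% interval, so 63% is not excluded there. The highest two-sided level at which 16/20 still excludes 63% is 1 − 2 × 0.0859 = 0.828.

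**Step 3: find the count needed at 90%.** P(X ≥ 17 | 20, 0.63) = 0.030, which is below 0.05. The 90% interval for 17/20 is 65.6% to 95.8%. The required count therefore moves from 16 to 17. If the true ORR is 80%, the chance of reaching that count falls from P(X ≥ 16) = 0.630 to P(X ≥ 17) = 0.411.

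**Step 4: compare with the backbone regimen.** Section 1.2 gives an ORR of 60% for atezolizumab plus carboplatin and etoposide in the pivotal trial. The 80% lower bound of 63.9% clears 60%. The 90% bound of 59.9% just fails to: P(X ≥ 16 | 20, 0.60) = 0.051. The plan does not name 60% as a threshold, but it is the comparison a reader of a single-arm cohort is likely to make.

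**Step 5: compare the two tables in Section 6.1.** Table 14 contains (0%, 22%), (2%, 28%), (7%, 40%) and (14%, 51%). These equal the exact 90% intervals for 1, 2, 4 and 6 out of 20. On that reading, Section 6.1 shows two different intervals for 1/20 and for 2/20: (1%, 18%) and (3%, 24%) in Table 13, against (0%, 22%) and (2%, 28%) in Table 14. The row labels of Table 14 are missing from the text available here, so the pairing is by calculation. The remaining entry, (0%, 16%), does not match 0/20, for which the upper limit is 13.9%; nothing here depends on it.

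**The case against.** The strongest reply is that no sentence in the plan is false. Section 6.1 labels its intervals as 80% each time, and a plan may illustrate precision at one level and report at another. Nothing is decided on 63%: there is no null rate, success criterion or go/no-go rule attached to it, no interim analysis is planned, and the aim is described as preliminary efficacy. The report will carry the pre-specified 90% interval either way. The maintenance-only sentence is untouched, because a single response excludes 0% at any level. Table 14 concerns adverse events, for which a different level would not in itself be an error.

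Most of this stands, and it limits the weight of the point. Type I error, power, sample size and analysis method are not affected, and the Table 14 comparison is only supporting evidence. What does not stand is the idea that the label settles the matter. The two levels concern the same endpoint in the same 20 patients, the plan gives no reason for the difference, and a statement about what the data will rule out is read as describing the reported result. The objection is right that explaining the 80% level would also be an acceptable repair.

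**Conclusion.** The point holds. It is an internal inconsistency in confidence level, not a calculation error. At the planned 90% Clopper-Pearson level, an observed 16/20 has a lower bound of 59.9% instead of 63.9% and an interval width of 33.0 instead of 27.0 percentage points. It does not rule out 63%; 17/20 is the smallest count that does.

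This rests on two things: n is exactly 20, and the method is the exact one named in Section 6.5.1. Other 90% methods give different lower bounds for 16/20 (Wilson 62.2%, Jeffreys 62.7%, Wald 65.3%), but the plan does not use them. The correction should be made because it concerns the only precision figure for the primary endpoint. It does not threaten the validity of the trial.

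**What to change.** Restate the ORR part of Section 6.1 and Table 13 at the two-sided 90% exact level:

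- 5%: (0.3%, 21.6%)
- 10%: (1.8%, 28.3%)
- 70%: (49.2%, 86.0%)
- 75%: (54.4%, 89.6%)
- 80%: (59.9%, 92.9%)

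In whole per cents these are (0%, 22%), (2%, 28%), (49%, 86%), (54%, 90%) and (60%, 93%). One decimal is better: rounding hides that 60% is not excluded at 16/20, and it shows the lower bound for 1/20 as 0%, which would seem to contradict the maintenance-only sentence.

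Replace the induction-plus-maintenance sentence with: *Assuming an observed ORR of 80% (16/20), the lower bound of the two-sided 90% exact CI is 59.9%.* The maintenance-only sentence needs only its level changed.

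Alternatively, keep 80%, give the reason for using it in planning, and show the 90% limits beside it.

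Either way the cost is one paragraph and one table row. The sample size, conduct and analysis stay as they are; the stated precision becomes somewhat less favourable.

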6.2 SUMMARIES OF CONDUCT OF STUDY

Enrollment, study drug administration, and discontinuation from the study will be summarized separately for the maintenance arm (Arm A) and the induction arm (Arm B) of the dose-escalation phase (by dose and overall) and for the dose-expansion phase. The reasons for study drug discontinuation will also be tabulated. Major protocol deviations, including major deviations with regard to the inclusion and exclusion criteria, will be summarized.

6.3 SUMMARIES OF DEMOGRAPHIC AND BASELINE CHARACTERISTICS

Demographic and baseline characteristics (including age, sex, ECOG performance status, and lung cancer history) will be summarized using means, standard deviations, medians, and ranges for continuous variables and proportions for categorical variables, as appropriate. Summaries will be presented separately for the maintenance arm (Arm A) and the induction and maintenance arm (Arm B) of the dose-escalation phase (by dose and overall) and for the dose-expansion phase.

6.4 SAFETY ANALYSES

The safety analysis population will consist of all enrolled patients who received at least one dose of study treatment, with patients grouped according to treatment received.

Summaries of safety will be presented separately for the maintenance arm (Arm A) and the induction and maintenance arm (Arm B) of the dose-escalation phase (by dose and overall) and for the dose-expansion phase.

6.4.1 Analyses of Exposure, Adverse Event, Laboratory, Vital Sign, and ECG Data

Safety will be assessed through summaries of exposure to study treatment, adverse events, changes in laboratory test results, and changes in vital signs and ECGs.

Study treatment exposure (such as treatment duration, total dose received, and number of cycles and dose modifications) will be summarized with descriptive statistics.

All verbatim adverse event terms will be mapped to Medical Dictionary for Regulatory Activities (MedDRA) thesaurus terms, and adverse event severity will be graded according to NCI CTCAE v5.0. All adverse events, serious adverse events, adverse events leading to death, adverse events of special interest, and adverse events leading to study treatment discontinuation that occur on or after the first dose of study treatment (i.e., treatment-emergent adverse events) will be summarized by mapped term, appropriate thesaurus level, and severity grade. For events of varying severity, the highest grade will be used in the summaries. Deaths and cause of death will be summarized.

Relevant laboratory, vital sign (pulse rate, respiratory rate, blood pressure, pulse oximetry, and temperature), and ECG data will be displayed by time, with grades identified where appropriate. Additionally, a shift table of selected laboratory tests will be used to summarize the baseline and maximum postbaseline severity grade. Changes in vital signs and ECGs will be summarized.

6.5 EFFICACY ANALYSES

The analysis population for the efficacy analyses will consist of all enrolled patients in the dose-expansion cohort, with patients grouped according to their assigned dose levels and treatment schedules.

6.5.1 Primary Efficacy Endpoint

The primary efficacy objective for the Phase Ib dose-expansion cohort is to evaluate the preliminary efficacy of venetoclax in combination with atezolizumab as maintenance therapy or venetoclax in combination with atezolizumab, carboplatin, and etoposide as induction therapy followed by venetoclax plus atezolizumab as maintenance therapy on the basis of the following endpoint:

 ORR, defined as the proportion of patients with a CR or PR on two consecutive occasions ≥4 weeks apart, as determined by the investigator according to RECIST v1.1 criteria.

Patients with no disease assessments for any reason will be classified as nonresponders. An estimate of ORR with 90% exact CI will be presented using the method of Pearson Clopper.

6.5.2 Secondary Efficacy Endpoints

The secondary efficacy objective for the Phase Ib dose-expansion cohort is to evaluate the preliminary efficacy of venetoclax in combination with atezolizumab as maintenance therapy or venetoclax in combination with atezolizumab, carboplatin, and etoposide as induction therapy or venetoclax and atezolizumab as maintenance therapy on the basis of the following endpoints:

- DOR
- PFS
- OS
- PFS rate at 6 months
- OS rate at 1 year

